### 5. STUDY SUBJECTS

#### 5.1 Disposition of Subjects

A table of frequency counts and percentages of all subjects who are screened, randomized, and in each analysis population will be provided. Subject disposition including study completion status and reasons for early termination will be tabulated by treatment group and overall. A by subject listing will be provided.

#### 5.2 **Protocol Deviations**

Distribution of the types of protocol deviations and the number of subjects that deviate from the protocol will be tabulated for the treatment groups in the mITT population. Protocol deviations will also be tabulated by severity (e.g., minor or major). A listing of all protocol deviations will be provided.

#### 5.3 Demographic Characteristics

Descriptive statistics will be used to summarize the demographic characteristics (age, gender, race, ethnicity, height, weight, and Body Mass Index [BMI]) for the mITT population. A by subject listing will be provided.

#### 5.4 Baseline Characteristics

Baseline characteristics of mITT subjects including historical SARS-CoV-2 results, comorbidity, and pregnancy test will be listed and summarized by treatment group and overall if appropriate.

#### 5.5 Medical History

All medical conditions will be classified by system organ class (SOC) and preferred term (PT)

using the Medical Dictionary for Regulatory Activities (MedDRA). The number and percent of subjects with each medical condition will be presented for each SOC and PT for the mITT population.

### 5.6 Concomitant Medications

All concomitant medications collected will be coded using the World Health Organization (WHO) Drug Dictionary. The number and percent of mITT subjects using concomitant medications will be tabulated by Anatomical, Therapeutic, and Chemical (ATC) level 2 and by ATC level 4. If the ATC level 2 or 4 term is missing, the higher ATC level term will be used in the medication summary table and data listing.

Prior medications will be summarized separately from concomitant medications, for the overall mITT population.

Prior medications are defined as medications that ended prior to the date of study drug administration. Concomitant medications are defined as medications that started at any time but ended on or after the date of study drug administration, including those that are ongoing at study completion. In the case of a missing or partial end date/time, in order to determine whether a medication is prior or concomitant, the following conservative imputation rule will be used: the unknown portions of a medication end date/time will be imputed to the latest possible. The imputed medication end date/time will then be compared with the date of study drug administration to determine if the medication is prior or concomitant.

Note the imputed end date/time will only be used to determine whether a medication is prior or concomitant. The actual date/time reported on the electronic case report forms (eCRFs) will be presented in the listings.

### 6. EFFICACY ANALYSES

All efficacy analyses will be carried out using the mITT population. Data on all efficacy endpoints will be listed and tabulated if appropriate.

#### 6.1 Primary Efficacy Endpoint and Analysis

The primary efficacy analysis will be carried out on the mITT population. The analysis will be repeated using the ITT and PP population if different from the mITT population,

The primary efficacy variable is the proportion of asymptomatic subjects who remain asymptomatic through Day 14. Subject clinical features/symptoms and radiographical evidence of pneumonia will be recorded in the database; the oxygen saturation by pulse oximetry on room air will be recorded daily through Day 14 by subject at home on the "SpO2 and Temperature Log", as well as on the "Patient's Measured Oxygen Saturation" eCRF at the protocol-specified healthcare provider visits. In the case when multiple SpO2 values are recorded on the same day, the lower value will be used for the analysis.

The null hypothesis is that the proportion of subjects who meet the primary endpoint in a given C19-IG 20% dose group (2 g and 1 g) will be no different than the proportion of subjects in placebo group; H0:  $\pi_t - \pi_c = 0$ . The alternative hypothesis is that the proportion of subjects who meet the primary endpoint at Day 14 in a given C19-IG 20% dose group will be different than the proportion

of subjects in placebo;  $H_1$ :  $\pi_t - \pi_c \neq 0$ .

Separate comparisons will be made for each C19-IG 20% dose group. If the 2 g dose group fails to demonstrate superiority compared to placebo at two-sided significance level of 5%, the test for 1 g dose group compared with placebo will be considered as exploratory rather than as confirmatory.

The proportion of subjects who meet the primary endpoint within each treatment group will be presented along with a two-sided exact (Clopper-Pearson) 95% confidence interval (CI).

The observed difference in the proportion of subjects who meet the primary endpoint between each C19-IG 20% dose group and placebo along with the exact unconditional 95% CI for risk difference will be calculated. The null hypothesis will be tested using Chi-square statistic and the p-value will be reported.

Sensitivity analysis on primary endpoint will be performed using the Cochran-Mantel-Haenszel (CMH) test, stratified by randomization strata (age <65 years versus  $\geq$  65 years). The common risk difference in the proportion of subjects meeting the primary endpoint between each C19-IG 20% dose group and placebo, together with the associated 95% CIs and p-value will be presented.

Subgroup analyses based on the presence of comorbidities associated with increased risk of serious COVID-19 will be performed on the primary endpoint using the method described above with Chi-square test, if appropriate. If data permit, a subgroup analysis based on the number of comorbidities (<2 comorbidities vs. >=2 comorbidities) will also be performed.

Subgroup analyses by perceived comorbidities will include the following conditions: Cancer; Chronic kidney disease; Chronic obstructive pulmonary disease (COPD); Heart conditions, such as heart failure, coronary artery disease, or cardiomyopathies; Immunocompromised state from solid organ transplant; Obesity (BMI of 30 kg/m2) or higher; Diabetes mellitus. The information of subject comorbidity will be recorded on the eCRF.

If for one or more subjects the actual treatment received is different from the randomized treatment and if deemed necessary, sensitivity analysis of the primary efficacy endpoint will be performed by repeating the primary efficacy analysis as described above in this section, but with subjects grouped according to the actual treatment received instead of the randomized treatment.

Data for COVID-19 clinical features/symptoms will be listed and summarized by treatment group at each time point. Radiographic evidence of pneumonia data will be presented in a listing.

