day 7, ranging in severity from death to resumption of normal activities after discharge. It was analyzed with a proportional odds model, using all six categories to estimate a common odds ratio. An odds ratio greater than 1 indicated that, for a given category, patients in the hyperimmune IVIG group were more likely to be in a better category than those in the placebo group. There were 308 patients included in the primary analysis (156 hyperimmune IVIG, 152 placebo). Hyperimmune IVIG treatment produced a robust rise in hemagglutination inhibition titers against influenza A and smaller rises in influenza B titers. Based on the proportional odds model, the odds ratio on day 7 was 1.25 (95% CI 0.79–1.97; p=0.33). In subgroup analyses for the primary outcome, the odds ratio in patients with influenza A was 0.94 (0.55–1.59) and was 3.19 (1.21–8.42) for those with influenza B (interaction p=0.023). When administered alongside standard care (most commonly oseltamivir), hyperimmune IVIG was not superior to placebo for adults hospitalized with influenza infection. However, the investigators found a clinical benefit of hyperimmune IVIG for patients with influenza B which was supported by antibody affinity analyses, although it was considered that this finding warranted further confirmation (24).

Taken together these data in the context of existing experience with convalescent plasma in the COVID-19 pandemic, suggest the potential benefit of C19-IG 20% as a therapeutic intervention for asymptomatic outpatients infected with SARS-CoV-2 with age-related increased risk of progression to overt COVID-19. The ability to concentrate antibody and administer a potent dose in a smaller volume with no constraints regarding ABO compatibility are additional advantages in this regard.

Additionally, C19-IG 20% is manufactured from convalescent plasma units with anti-SARS-Cov-2 antibody titers ≥7.0 using the Architect-Abbott method or ≥10.0 using the Vitros-Ortho method. Thus, the product is targeted for highly concentrated antibody delivery.

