A hierarchical ordered testing procedure will be employed for handling the multiplicity issue to maintain the overall family-wised alpha level at 0.05 for comparisons between each dose and placebo. The null hypothesis for 1g vs placebo is tested only if the superiority for the 2g dose compared to placebo has been shown at a two-sided significance level of 5%. The order in which the null hypotheses are tested is predetermined as below:

- 1. H01: no difference between 2g and placebo on primary efficacy endpoint
- 2. H02: no difference between 1g and placebo on primary efficacy endpoint

The primary efficacy analysis will be carried out on the mITT population and repeated on the ITT and PP population (if different from the mITT population). Primary efficacy endpoint of proportion of asymptomatic subjects who remain asymptomatic will be compared between 2 doses of C19-IG 20% and Placebo by Fisher's exact test or Chi-square test. Sensitivity analysis stratified by age group will be performed using Cochran-Mantel-Haenszel (CMH) test. The first secondary efficacy endpoint of change in SARS-CoV-2 viral load (log10 copies/mL) from Baseline (Day 1) to Day 7 and to Day 14 will be analyzed by ANCOVA with treatment and randomization strata as fixed effects and baseline value as covariate. Other secondary and exploratory efficacy analyses will be analyzed by means of Kaplan-Meier survival estimates and curves and compared between treatment groups by means of the Log-rank test for time to event variables, analysis of covariance (ANCOVA) or Student's t test for normally-distributed variables or Wilcoxon rank-sum test for non-normally-distributed variables, Fisher's exact test or Chi-square test or CMH as appropriate for proportion variables.

Subgroup analysis based on the presence of comorbidities associated with increased risk of serious COVID-19 will be performed to explore the impact on the study outcomes. Subgroup analyses by perceived comorbidities will include the following conditions: Cancer; Chronic kidney disease; Chronic obstructive pulmonary disease (COPD); Heart conditions, such as heart failure, coronary artery disease, or cardiomyopathies; Immunocompromised state from

solid organ transplant; Obesity (BMI of 30 kg/m^2) or higher; Diabetes mellitus.

Detailed data handling and evaluation procedures will be described in the Statistical Analysis Plan (SAP).

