# 3. INVESTIGATIONAL PLAN

## 3.1 Study Design

This is a prospective, multi-center, randomized (1:1:1), double-blind study of C19-IG 20% at 1 of 2 dose levels versus Placebo in asymptomatic, ambulatory outpatients aged  $\geq$ 18 years who are SARS-CoV-2 positive. Participants will be stratified by age <65 years vs  $\geq$ 65 years of age. The study will enroll asymptomatic subjects with laboratory-confirmed novel coronavirus (SARS-CoV-2) infection as determined by qualitative PCR (reverse transcriptase [RT]-PCR), or other commercial or public health assay approved by regulatory authorities as a diagnostic for COVID-19 (inclusive of SARS-CoV-2 antigen testing or other approved rapid testing platforms) in any specimen obtained  $\leq$  5 days prior to randomized treatment ( $\leq$  5 days is the post-sampling timeframe from date specimen obtained to administration of blinded study drug). Every effort should be made to reduce this time interval to the minimum as nearly immediate treatment is key for successful intervention.

Approximately 801 subjects (267 per arm) will be randomized (1:1:1). Subjects randomized to C19-IG 20% will receive a blinded subcutaneous (SC) infusion on Day 1 at a dose of either 1 gram or 2 grams, according to the randomized dose assigned. Subjects randomized to Placebo will receive a SC infusion of sterile 0.9% sodium chloride injection, United States Pharmacopeia (0.9% NaCl, USP) or equivalent. Blinded study drug will be prepared and administered by an unblinded study nurse who is entirely independent of the evaluating study team with SC infusions using 2 separate syringes as follows:

- Placebo (*two* syringes each containing 5 mL 0.9% NaCl);
- 1 gram C19-IG 20% (one syringe containing 5 mL C19-IG 20% *Plus* one syringe containing 5 mL 0.9% NaCl)
- 2 grams C19-IG 20% (*two* syringes each containing 5 mL C19-IG 20%).

An independent DSMB will review interim safety data when approximately 399 patients have been randomized and treated with follow-up through Day 29 (approximately 133 patients per randomized group).

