# 3.2 Treatment

### 3.2.1 Randomization Scheme and Treatment Arm Assignment

Eligible subjects will be randomized 1:1:1 to Placebo or to C19-IG 20% via a SC infusion on Day 1 at a dose of either 1 gram or 2 grams, according to the randomized dose assigned. A central randomization stratified by age group (age <65 years versus  $\geq$  65 years) will be used for this study. Randomization will be centralized and will be performed via an Interactive Web Response System after subject inclusion. A randomization list containing the randomization numbers and the corresponding randomized treatment assignments will be generated and stored in a secured area that is only accessible to the randomization team.

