### 6.2 Secondary Efficacy Endpoints and Analyses

### Change in SARS-CoV-2 viral load

Change in SARS-CoV-2 viral load (log10 copies/mL) from Baseline to Day 7 and to Day 14 will be compared between each C19-IG 20% dose group and placebo using the analysis of covariance (ANCOVA) model, including the change from baseline value as a dependent variable; treatment group as a fixed effect; and baseline SARS-CoV-2 viral load value, age and gender as covariates. From this model, the LS means and 95% CIs for each treatment group, the treatment difference in the LS means, the 95% CI for the difference, and the associated p-value will be presented at Day 7 and Day 14.

Subgroup analyses based on the presence of comorbidities associated with increased risk of serious

COVID-19 will be performed on change in SARS-CoV-2 viral load using the method described above with ANCOVA model at Day 7 and Day 14. If data permit, a subgroup analysis based on the number of comorbidities (<2 comorbidities vs. >=2 comorbidities) will also be performed.

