- If admitted to ICU post randomization: Duration of ICU stay through Day 29.
- Proportion of subjects requiring invasive mechanical ventilation through Day 29.
- If requiring invasive mechanical ventilation post randomization: Duration of invasive mechanical ventilation through Day 29.
- All-cause mortality through Day 29.
- Incidence of critical COVID-19 illness, defined as any one of the following: (a) requiring ICU admission or ICU level of care\*, (b) invasive mechanical ventilation, or (c) resulting in death by Day 29.
- Length of time to clinical progression to critical COVID-19 illness through Day 29 (defined as the time to death, invasive mechanical ventilation, or ICU admission/requiring ICU level of care).

After this interim analysis, the 1 gram dose arm may be terminated, the trial may be terminated (if the 2 gram dose is discontinued, the 1 gram dose will also be terminated), or the study will continue as originally planned unless discontinued for business or feasibility reasons in a setting of changing epidemic dynamics in the geographic catchment of the trial.

The futility analysis will not inflate the type I error since the trial will not be stopped to claim efficacy. The primary and key secondary efficacy outcomes will be analyzed using the methods described above in Section 6.1 and 6.2. No subgroup or sensitivity analyses are planned for the futility analysis.

Suppose at the time of data-cut for the futility analysis,  $x_0$  subjects meet the primary efficacy endpoint among  $m_0$  subjects in the placebo group, and  $x_1$  subjects have events among  $m_1$  subjects in the treatment group (1 gram or 2 grams C19-IG 20%). Let  $\tilde{p}_g = x_g/m_g$  for group g = 0, 1; and  $\tilde{p} = (x_0 + x_1)/(m_0 + m_1)$ .  $Z_1 = \frac{\tilde{p}_1 - \tilde{p}_0}{\sqrt{(m^{-1} + m^{-1})\tilde{p}(1 - \tilde{p})}}$  is the z-score corresponding to the Chi-

square statistic.

Let the final sample size be  $n_0$  and  $n_1$  in the placebo and treated (1 gram or 2 grams C19-IG 20%)

0

1

groups respectively. Let  $Z_{1-\alpha/2}$  be the 1-  $\alpha/2 = 97.5\%$  percentile of the normal distribution, which

can be calculated as the PROBIT function in SAS. Let  $t = (n_0^{-1} + n_1^{-1})/(m_0^{-1} + m_1^{-1})$ . The conditional power (CP) for the primary efficacy endpoint (each of C19-IG 20% dose groups compares to placebo) will be calculated using the formula:

$$CP = 1 - \Phi \left( \frac{Z_{1-\alpha/2} - Z_1/\sqrt{t}}{\sqrt{1-t}} \right)$$

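### Randomisation is stratified by age, but the primary test, its interval and the conditional-power z-score ignore the strata, at a small power cost if age is prognostic; separately, the viral-load model differs between protocol and SAP

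*SAP*

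**What the plan says.** SAP 3.2.1 sets out "A central randomization stratified by age group", <65 versus ≥65 years, and names no other factor; protocol 4.3.2 agrees.

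For the primary endpoint, SAP 6.1 gives the crude difference in proportions with an exact unconditional 95% interval and then says: "The null hypothesis will be tested using Chi-square statistic and the p-value will be reported". The stratified analysis follows as a supporting one: "Sensitivity analysis on primary endpoint will be performed using the Cochran-Mantel-Haenszel (CMH) test, stratified by randomization strata", reported with a common risk difference. Protocol 9.1 has the same hierarchy (Fisher's exact or chi-square as primary, age-stratified CMH as sensitivity).

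In SAP 9, conditional power is computed from a statistic built on pooled proportions that "is the z-score corresponding to the Chi"-square test. No sensitivity analyses are planned at that look.

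On the role of age, protocol 2.3.1 speaks of "asymptomatic outpatients infected with SARS-CoV-2 with age-related increased risk of progression to overt COVID-19" but gives no figure.

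For the first secondary endpoint, protocol 9.1 says change in viral load "will be analyzed by ANCOVA with treatment and randomization strata as fixed effects and baseline value as covariate". SAP 6.2 instead specifies "treatment group as a fixed effect; and baseline SARS-CoV-2 viral load value, age and gender as covariates".

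**The concern.** Stratified randomisation balances the arms on age. If age also predicts the outcome, the true sampling variance of the treatment difference is the within-stratum variance. An unstratified test uses the total variance, which also contains the spread between age groups. Its standard error is then too large: true type I error falls below 5%, and power is lower than the design could deliver. At the interim the same understated z-score feeds the conditional power, so a futility reading is slightly pessimistic, with no stratified figure planned beside it.

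The viral-load issue is different in kind. Two models are prespecified for one endpoint. Gender is not a stratification factor, the SAP does not say whether age enters as a continuous variable or as the randomised group, and the SAP revision table does not list the change. Choosing between the models after unblinding could look data-driven.

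**Working it through.** **Inputs from the documents.** 80% of placebo and 90% of active subjects remain asymptomatic; about 240 evaluable and 267 randomised per arm; sizing at alpha 0.025 with 80% power (protocol 9.2, SAP 10); testing at two-sided 0.05 (SAP 4 and 4.5).

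**Inputs assumed, because the documents do not give them.** Share aged ≥65: 10–40%. Placebo gap between age groups in the percentage remaining asymptomatic: 0–30 points. Treatment halves the failure risk in both age groups. Arms are balanced within strata.

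**1. The plan's own figure.** n = [p₁(1−p₁) + p₂(1−p₂)] × (z₀.₉₈₇₅ + z₀.₈₀)² / d² = (0.16 + 0.09) × (2.2414 + 0.8416)² / 0.10² = 237.6, i.e. 238 per arm as stated. 240/0.9 gives 267, and 3 × 267 = 801. At the two-sided 0.05 level actually used for testing, the unstratified power by normal approximation is 86.8% with 240 per arm and 90.1% with 267.

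**2. Variance, with 30% aged ≥65.** Total variance is p(1−p); within-stratum variance is Σ w p(1−p) over the two age groups.

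- Gap 20 (placebo 86%/66%, active 93%/83%). Within: placebo 0.7×0.86×0.14 + 0.3×0.66×0.34 = 0.1516; active 0.7×0.93×0.07 + 0.3×0.83×0.17 = 0.0879. Ratio: (0.16 + 0.09)/(0.1516 + 0.0879) = 1.044, so the SE is 2% too large.
- Gap 30 (placebo 89%/59%, active 94.5%/79.5%). Within: 0.1411 and 0.0853. Ratio: 0.25/0.2264 = 1.104, so the SE is 5% too large.

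Under the null the ratios are 0.16/0.1516 = 1.055 and 0.16/0.1411 = 1.134. The approximate true size of the chi-square is 2[1 − Φ(1.96√1.055)] = 4.4% and 2[1 − Φ(1.96√1.134)] = 3.7%.

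**3. Simulation.** 400,000 trials per cell, 240 per arm, two-sided 0.05, no continuity correction, 30% aged ≥65:

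| Placebo gap (points) | Chi-square power | CMH power | Chi-square size | CMH size |
|---|---|---|---|---|
| 0 | 87.4% | 87.4% | 5.0% | 5.0% |
| 10 | 87.5% | 87.7% | 4.9% | 5.0% |
| 20 | 87.9% | 88.6% | 4.5% | 5.0% |
| 30 | 88.4% | 90.1% | 3.7% | 5.0% |

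With 10% aged ≥65 the CMH gain is 0.4 points (gap 20) and 0.8 (gap 30). With 40% it is 0.9 and 1.9. At gaps of 0–5 points it is essentially zero.

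**4. A different effect model.** With a common odds ratio in place of halved risk, 20% aged ≥65 gives gains of 0.7 points (gap 20) and 1.5 (gap 30). The most extreme case tried, 40% aged ≥65 with a 40-point gap, gives 92.9% versus 89.7%, a gain of 3.2 points.

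**5. Interval.** At gap 20 with 30% aged ≥65, the Mantel-Haenszel interval averages 12.4 points wide with 95.0% coverage; the unstratified Wald interval averages 12.6 with 95.4%.

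**6. Conditional power.** CP = 1 − Φ[(1.96 − Z₁/√t)/√(1−t)]. Taking t = 0.5 and Z₁ = 1.0 for illustration: (1.96 − 1.414)/0.707 = 0.772, so CP = 22.0%. Raising Z₁ by the SE excess in step 2 (2% or 5%) gives about 23% or 25%.

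**7. Viral load.** Protocol 9.1: treatment, randomisation strata, baseline. SAP 6.2: treatment, baseline, age, gender. Both models adjust for age in some form, so no power loss is claimed here; the point is that the two texts disagree.

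**The case against.** The best counter-argument is that this is a preference between two valid analyses. Protocol and SAP agree on the unstratified primary test, type I error is not inflated, and the stratified result will be reported anyway. The SAP 2.0 revision table records changes to these very tests, so the choice looks deliberate. All of that stands.

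Support for age being prognostic is also thin. The sentence in protocol 2.3.1 describes the trial population, not a <65 versus ≥65 contrast; protocol 2 applies the same idea to everyone aged ≥18 and names older age as a risk factor for death, not for symptoms by Day 14. This too stands: the age gaps above are assumptions, and with no age effect CMH gains nothing.

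At the interim, the formula matches the planned final test and the SAP states no conditional-power cutoff, so no changed decision can be shown. For viral load, SAP 4.5 makes no multiplicity adjustment for secondary endpoints, and the protocol leaves detailed methods to the SAP. That limits the consequences but does not remove the contradiction.

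These arguments limit the weight of the point. They do not give a reason to prefer the unstratified analysis beyond its exact interval, which can be kept as a sensitivity analysis.

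**Conclusion.** Both parts hold. The first concerns efficiency, not validity: at 240 per arm, 80% versus 90% and 10–40% aged ≥65, the power given up is about 0.1–0.2 points at a 10-point placebo age gap, 0.4–0.9 at 20 and 0.8–1.9 at 30. Chi-square size falls to 4.8–4.4% at gap 20 and 4.5–3.5% at gap 30, while CMH stays at 5.0%. Chi-square power remains about 87–89%, above the 80% target, so the trial's ability to answer its question is not in doubt. The size depends wholly on an age mix and an age effect that the documents do not supply.

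The second part, the conflicting viral-load models, needs no assumption. The change should be made because it is almost free, not because the plan fails without it.

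**What to change.** Before the interim data cut and unblinding:

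- In SAP 6.1 and protocol 9.1, make the CMH test by randomised age group primary, with the Mantel-Haenszel common risk difference and its 95% interval, and name the variance estimator.
- Keep the unstratified chi-square and the exact unconditional interval as sensitivity analyses.
- In SAP 9, put the CMH z-score into the conditional-power formula so that it matches the new final test.
- Settle on one viral-load ANCOVA in protocol 9.1 and SAP 6.2, for example by including the randomisation strata; state how age is coded, and record the change in the revision table.

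The cost is wording only: no new data are needed, and both primary-endpoint tests are already written in SAP 6.1. The one drawback is that the primary interval is no longer exact; simulated Mantel-Haenszel coverage was 94.9–95.2%.
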